8.2.1.1. Adverse Events of Special Interest

Adverse events (AEs) of special interest (AESI) have been defined as AEs which have specified areas of interest for FF, VI, or UMEC or for the COPD population. A list of Standardized Medical Dictionary for Regulatory Affairs (MedDRA) Queries (SMQs) and other groupings for AESI is provided in Section 10.6.3.

8.2.1.2. Pneumonia

Summaries of pneumonia will include data from the Pneumonia Details CRF form.

8.2.1.3. Vital Signs

Vital signs are collected at Screening (Visit 1) and pre-dose at Week 4, Week 24 or at the Early Withdrawal Visit. Vital signs collected at Early Withdrawal and at the onset of a pneumonia event will be included in ‘minimum/maximum post-baseline’ (see Section 10.6.3 for the definition) summaries but will not be summarized separately.

8.2.1.4. ECGs

12-Lead ECGs are collected at Screening (Visit 1) and approximately 15-45 min after dosing at Week 24 or at the Early Withdrawal Visit. All ECG data present in the database will be considered valid and will be reported (even if the ECG had a technical error). ECGs collected at Study Treatment Discontinuation will be included in summary of ECG finding where ‘worst case post-baseline’ summarized but will not be summarized separately.

8.2.1.5. Pregnancy

Any pregnancies reported during the study will be summarized in case narratives. Any pregnancy complication or elective termination of a pregnancy for medical reasons will be recorded as an AE or SAE and included in summaries and listings of AEs/SAEs.

10. APPENDICES

Section	Appendix
RAP Section 4 : Analysis Populations	
Section 10.1	Appendix 1: Protocol Deviation Management and Definitions for mPP Population
RAP Section 5 : General Considerations for Data Analyses & Data Handling Conventions	
Section 10.2	Appendix 2: Time and Events
Section 10.3	Appendix 3: Assessment Windows
Section 10.4	Appendix 4: Treatment States & Phases
Section 10.5	Appendix 5: Data Display Standards & Handling Conventions 
 • Study Treatment & Sub-group Display Descriptors • Baseline Definitions & Derivations • Reporting Process & Standards
Section 10.6	Appendix 6: Derived and Transformed Data 
 • General, Study Population & Safety • Efficacy
Section 10.7	Appendix 7: Premature Withdrawals & Handling of Missing Data 
 • Premature Withdrawals • Handling of Missing Data
Section 10.8	Appendix 8: Multicentre Studies 
 • Laboratory Values • ECG • Vital Signs
Section 10.9	Appendix 9: Examination of Covariates and Subgroups
Section 10.10	Appendix 10: Multiple Comparisons and Multiplicity
Section 10.11	Appendix 11: Model Checking and Diagnostics for Statistical Analyses
Other RAP Appendices	
Section 10.12	Appendix 12: Abbreviations & Trade Marks
Section 10.13	Appendix 13: List of Data Displays

10.1. Appendix 1: Protocol Deviation Management and Definitions for mPP Population

10.1.1. Exclusion of Data from the ITT Analyses

In general, all data recorded for subjects who were randomised (excluding those randomised in error) will be included in ITT analyses. The following will result in exclusion of data from ITT analyses:

Spirometry data are excluded from ITT analyses if the actual time of assessment is after the time of dosing on that day or if albuterol/salbutamol was used within 4h of the assessment on that day.

10.1.2. Exclusions from mPP Population

The full list of protocol deviations collected on the eCRF is in the PDMP.

The mPP Population is the primary analysis population, comprising all subjects from ITT population with the exception of:

- Full exclusion: subjects who have a full protocol deviation considered to impact primary endpoint (trough FEV1)
 - Eligibility criteria (those that impacts primary endpoint as listed in PDMP, [Appendix 2](#)) not met
 - Treatment non-compliance (overall compliance <80% or >120% over the 24-week treatment period, based on active treatment)
 - Randomisation criteria not met
 - Pneumonia or moderate/severe COPD exacerbation during run-in
 - Any change to COPD maintenance medications (including dosage and regimen) during the run-in
 - Antibiotics for respiratory tract infections during the run-in
- Partial exclusion: subjects who have a protocol deviation considered to impact primary endpoint. Trough FEV1 assessments collected after the incidence of the protocol deviation will be excluded from primary analysis.
 - Subject received incorrect container which contains incorrect study treatment.
 - Subjects took prohibited medication during treatment period, as detailed in PDMP [Appendix 3](#) Prohibited Medication.

- Partial exclusion: other events (not a protocol deviation) considered to impact the primary endpoint. Trough FEV1 assessments collected on or after the event start date will be excluded from primary analysis.
 - Subjects had a moderate/severe COPD exacerbation
 - Subjects had pneumonia.
 - Subjects who were unblinded by GCSP due to safety concerns.

Note: Subjects who received incorrect treatment and non-compliance based on active treatment will be identified as important PDs and flagged as PP exclusionary following treatment unblinding. These PDs will be flagged as PP exclusionary in ADaM DV dataset and will be included in summary of exclusion from mPP population table.

10.2. Appendix 2: Time & Events

Protocol Activity	Pre-Screen	Screen	Treatment				Follow Up	
	Visit 0 Pre-screen	Visit 1 Screening	Visit 2 Randomisation	Visit 3	Visit 4	Visit 5	Early Withdrawal Visit	Safety Follow-up Contact
Study Week		Week -2	Week 0	Week 4	Week 12	Week 24		1 week Fw-up
Window		-3/+8d		-4/+2d	-8/+6d	-8/+6d		-1/+4d
Written Informed Consent ^a	X	X						
Genetic Informed Consent ^b	X	X						
Demography ^c	X	X						
Medical History, including cardiovascular history		X						
COPD and Exacerbation History		X						
Concomitant Medication Assessment	X	X	X	X	X	X	X	X
Inclusion/Exclusion Criteria		X						
Randomisation Criteria			X					
Smoking History		X						
Smoking status		X				X	X	
Smoking Cessation Counselling		X				X	X	
Register Visit in IRT/ RAMOS NG ^d		X	X	X	X	X	X	
Reversibility Testing ^e		X						
Spirometry			X ^f	X ^f	X ^f	X ^f		
Device training and registration		X	X					
Exacerbation Assessment		X	X	X	X	X	X	X
SGRQ-C ^g			X		X	X		
BDI ^g			X					
TDI ^g					X	X		
CAT ^g		X						
eDevice close out ^h			X			X	X	
Physical examination ⁱ		X				X	X	
Adverse Events Assessment		X	X	X	X	X	X	X
Vital signs ^j		X		X		X	X	
ECG		X				X ^k	X ^k	
Chest X-ray ^l		X						
Pulse oximetry ^m			X					
Blood draw for PK					X ⁿ	X ^o		
Blood Draw for Genetics research						X ^p		

Protocol Activity	Pre-Screen	Screen	Treatment				Follow Up	
	Visit 0 Pre-screen	Visit 1 Screening	Visit 2 Randomisation	Visit 3	Visit 4	Visit 5	Early Withdrawal Visit	Safety Follow-up Contact
Study Week		Week -2	Week 0	Week 4	Week 12	Week 24		1 week Fw-up
Window		-3/+8d		-4/+2d	-8/+6d	-8/+6d		-1/+4d
Haematology/biochemistry ^q		X				X	X	
Urine Pregnancy Test ^r		X		X	X	X	X	
Hepatitis B and C tests		X						
Dispense study treatment			X	X	X			
Administer study treatment in clinic ^s			X	X	X	X	X	
Assess study treatment compliance				X	X	X	X	
Collect study treatment				X	X	X	X	
Dispense albuterol/salbutamol		X	X	X	X			
Collect albuterol/salbutamol			X	X	X	X	X	
Issue/review paper diary ^t		X	X	X	X	X	X	

- a. Informed consent must be conducted at the Pre-screen Visit prior to performing any study procedures including the changing or withholding of medications. The (IC) may be given at Screening Visit 1 if the subject does not take or has not taken any protocol excluded medications.
- b. Genetics research consent may be obtained at the same time as the study IC and must be obtained prior to obtaining a genetic blood sample.
- c. Demography may be captured at either the Pre-screen Visit or Screening Visit (for subjects who do not have a Pre-screen Visit).
- d. The IRT will be used for randomisation, emergency unblinding and study treatment supply management (Please refer RAMOS NG IRT manual for more information)
- e. At Screening Visit 1 both pre and post-bronchodilator spirometry will be conducted. Pre-bronchodilator spirometry will be performed prior to the subject taking their morning dose of their usual COPD treatment, between 6am and 11am and after withholding rescue albuterol/salbutamol for ≥ 4 hours.
- f. At Visits 2-5 (and the Early Withdrawal Visit), pre-bronchodilator spirometry will be performed prior to taking the morning dose of study treatment, between 6am and 11am and after withholding rescue albuterol/salbutamol for ≥ 4 hours.
- g. Patient reported assessments should be conducted in the following order and before other study assessments: SGRQ-C, BDI/TDI.
- h. Close out eDevice for any subject who fails to randomize, withdraws early, or completes Visit 5.
- i. Physical examination may include height, weight, blood pressure, temperature, heart rate.
- j. Vital signs must be performed prior to spirometry and prior to taking morning dose of study medication.
- k. ECG to be obtained 15 - 45 minutes post-dose at treatment Visit 5 and Early Withdrawal Visit (if possible). If a subject is not dosed at Early Withdrawal, then an ECG can be taken at any time during the visit
- l. Chest X-ray (PA and lateral) is required at Screening (or historical x-ray obtained within 3 months prior to Screening) and at anytime there is a suspected pneumonia or a mod/severe exacerbation.
- m. Pulse oximetry must be performed at V2 and anytime there is a suspected pneumonia or a moderate or severe exacerbation.
- n. PK subset A: PK samples of 120 subjects at selected sites, to be obtained at two time points at Visit 4: pre-dose and in the window 5 to 15 minutes post-dose.
PK subset B: PK samples of 60 subjects at selected sites, to be obtained and Visit 4: pre-dose, 5-15min, 45-90min, 2.5-4h, 6-8h, 10-12h, 23-24h post-dose.
- o. PK subset A: PK samples of 120 subjects at selected sites, to be obtained at two time points at Visit 5: 5 to 15 minutes post-dose and 45 to 90 minutes post-dose.
- p. The genetics blood sample should be taken at V5 or at any visit after Randomisation (V2).
- q. Haematology and chemistry panels will include liver chemistry, and potassium and glucose levels.
- r. All female subjects of child bearing potential will have a urine pregnancy test at each visit except Visits 2 and follow-up.
- s. Subjects must withhold their morning dose of study treatment at each clinic visit and not take their study treatment dose until instructed to do so by study staff.
- t. Subjects will be issued a paper diary, at screening and other clinic visits (if required) in order to note any changes to concomitant medications and/or incidence of adverse events that may have occurred between clinic visits.

10.3. Appendix 3: Assessment Windows

In general, data will be reported according to the nominal time of clinic visits and assessments as specified in the protocol. For example, if a subject recorded values for the Week 4 visit that were actually made on the 21st day of treatment, they will be presented as Week 4 values in the summary tables.

Subjects that permanently stop study medication early between scheduled clinic visits should undergo all assessments listed for the Early Withdrawal Visit. Data collected at this visit will be listed and used in summary or analysis tables as part of the ‘worst case post baseline’ summary/analysis if appropriate.

Subjects that permanently stop study medication early at the time of a scheduled study visit will have data collected in the eCRF as part of the scheduled study visit.

10.4. Appendix 4: Treatment States and Phases

Assessments and events will be classified according to time of occurrence relative to the start and/or stop date of the study treatment. The ‘worst case-post baseline’ derivation for summaries of data up to Week 24 will consider all scheduled and unscheduled measurements that have been assigned a treatment phase of ‘On-treatment’.

10.4.1. Treatment Phase for Concomitant Medication Data

COPD medication combinations taken at screening will include all COPD medications that were taken on the day of the screening visit, excluding medications that stopped on the day of the screening visit. Calculation of stratum, i.e. long-acting bronchodilator usage per day during the run-in (none, one or two long-acting bronchodilators per day), will also be based on the COPD medication taken on the day of the screening visit. If the calculated stratum is different to the randomized stratum, the calculated stratum will be used as a covariate in all analyses, but both values will be listed. Treatment phases for summaries of COPD and non-COPD concomitant medications will be defined as follows:

Definition	Treatment Phase		
	Run-in	On-treatment	Post-treatment
Subject did not take study treatment (e.g. run-in failures) and conmed stop date > date of Screening or variable that asks if conmed is ongoing (refer hereafter as goingmed) is “yes”	Y		
(Conmed start date < treatment start date or variable that asks if medication taken prior to study is “yes” (refer hereafter as priormed)) and date of Screening < conmed stop date < treatment start date	Y		
(Conmed start date < treatment start date or priormed is yes) and treatment start date ≤ conmed stop date ≤ treatment stop date	Y	Y	
(Conmed start date < treatment start date or priormed is yes) and (conmed stop date > treatment stop date or goingmed is “yes”)	Y	Y	Y
(Treatment start date ≤ conmed start date < treatment stop date and treatment start date ≤ conmed stop date ≤ treatment stop date) or (Treatment start date = conmed start date = conmed stop date = treatment stop date)		Y	
([Treatment start date ≤ conmed start date < treatment stop date] or [Treatment start date = conmed start date = treatment stop date]) and (conmed stop date > treatment stop date or		Y	Y

Definition	Treatment Phase		
	Run-in	On-treatment	Post-treatment
goingmed is Yes)			
Conmed start \geq treatment stop date and treatment start date \neq treatment stop date			Y

NOTES:

- A concomitant medication will be classed in every period of the study in which it was taken (e.g., run-in, on-treatment or post-treatment).
- See Section 10.7.2.1 for handling of partial dates.
- If the study treatment stop date is missing, it will be imputed as described in Section 10.6.1.
- Medications that stopped prior to Screening will not be assigned a treatment phase and will not be summarized.

10.4.2. Treatment Phase for Other Data

Treatment phases for assessments scheduled at a set time will be defined according to the planned relative time of the assessment.

Any events/assessments for subjects not in the ITT population will be assigned a Pre-treatment phase.

For all events and assessments where time is recorded, pre-treatment and on-treatment and post-treatment phases will be defined as below:

Treatment Phase	Definition
Pre-treatment	Event onset date/time or assessment date/time < treatment start date/time.
On-treatment	Treatment start date/time \leq event onset date/time or assessment date/time \leq treatment stop date + 1 day, or any event/assessment with a missing or partial onset date unless there is evidence it was not on-treatment.
Post-treatment	Event onset date/time or assessment date/time \geq treatment stop date + 2 and event onset date/time or assessment date/time \leq study conclusion date Note: the study conclusion date reflects the safety F/U contact for study treatment completers.

For all events and assessments (with the exception of concomitant medications) where time is not recorded, the pre-treatment, on-treatment and post-treatment phases will be defined as below:

Treatment Phase	Definition
Pre-treatment	Event onset date or assessment date < treatment start date.
On-treatment	Treatment start date ≤ event onset date or assessment date ≤ treatment stop date + 1 day or any event/assessment with a missing or partial onset date unless there is evidence it was not on-treatment.
Post-treatment	Event onset date or assessment date ≥ treatment stop date + 2 and event onset date or assessment date ≤ study conclusion date Note: the study conclusion date reflects the safety F/U contact for study treatment completers.

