6. STUDY TREATMENT

6.1. Investigational Product and Other Study Treatment

The term 'study treatment' is used throughout the protocol to describe any combination of products received by the subject as per the protocol design. Study treatment may therefore refer to the individual study treatments or the combination of those study treatments.

All treatments will be delivered by ELLIPTA containing 30 doses.

Following the run-in period, eligible subjects will be randomized (1:1) to one of the following double-blind treatment groups:

- FF/UMEC/VI 100mcg/62.5mcg/25mcg and placebo, both via the ELLIPTA once daily in the morning
or,
- FF/VI 100mcg/25mcg and UMEC 62.5mcg, both via the ELLIPTA once daily in the morning.

The randomisation will be stratified based on long-acting bronchodilator usage during the run-in (none, one or two long-acting bronchodilators per day).

The ELLIPTA contains 30 doses (FF/UMEC/VI, FF/VI, UMEC or placebo). Each subject will be instructed on the proper use of the ELLIPTA and will inhale once from each of their ELLIPTAs each morning for the duration of the 24-week treatment period. Subjects will self-administer their first dose of blinded study treatment in the clinic during Randomisation (V2). On the morning of the other study clinic visits, subjects will refrain from taking their morning dose of study treatment until instructed to do so by clinic personnel. Subjects will take their last dose of study treatment at the clinic at Visit 5 and a safety follow-up will be conducted either by phone call or clinic visit approximately one week later. Subjects will discontinue their existing COPD medication on the day before Randomisation (V2) but may continue their study-supplied rescue albuterol/salbutamol.

There are no plans to provide the study drug for compassionate use following study completion.

Descriptions of the study treatments administered via the ELLIPTA are provided in [Table 2](#).

Table 2 Description of study treatment inhalation powder via ELLIPTA

FF/UMEC/VI	First strip	Second strip
		FF blended with lactose
Dosage Form	ELLIPTA with 30 doses (2 strips with 30 blisters per strip)	
Unit Dose Strengths	100mcg per blister	62.5 mcg per blister UMEC, 25 mcg per blister VI
Physical description	Dry white powder	Dry white powder
Route of Administration	Inhaled	
FF/VI	First strip	Second strip
	FF blended with lactose	VI blended with lactose and magnesium stearate

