4. ANALYSIS POPULATIONS

Population	Definition / Criteria	Analyses Evaluated
All Subjects Enrolled (ASE)	
 • All subjects for whom a record exists in the study database, including screen failures and any subject who was not screened but experienced an SAE between the date of informed consent and the planned date of the Screening visit. 	
 • Subject Disposition • Reason for withdrawal prior to randomisation • Inclusion, exclusion and randomisation criteria deviations • SAEs for non-randomised subjects
Intent-to-Treat (ITT)	
 • All randomized subjects, excluding those who were randomized in error. A subject who is recorded as a screen or run-in failure and also randomized will be considered to be randomized in error. Any other subject who receives a randomization number will be considered to have been randomized. 	
 • Study Population • Efficacy • Health-related Quality of Life • Inhaler Assessments • Safety
Modified Per Protocol (mPP)	
 • All subjects in the ITT Population who do not have a full protocol deviation considered to impact efficacy. • Data following a moderate/severe COPD exacerbation or pneumonia will be excluded from analysis due to the potential impact of the exacerbation or the medications used to treat it • Subjects with partial protocol deviations considered to impact efficacy will be included 	
 • Primary treatment comparison of the primary endpoint only

Population	Definition / Criteria	Analyses Evaluated
	in the mPP Population but will have their data excluded from analyses from the time of deviation onwards.	

NOTES : Please refer to [Appendix 13](#): List of Data Displays which details the population to be used for each displays being generated.

In the event one or more investigators are withdrawn from the study due to concerns over protocol deviation then a further population will be defined which will consist of all subjects in the ITT population excluding subjects from those investigative sites. This population will be used to perform additional sensitivity analysis for the primary efficacy endpoint only, and will only be defined if the combined enrolment at these sites exceeds $\geq 2\%$ of the overall ITT study enrolment.

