10.13.7. Safety Tables

Safety Tables			
No.	Population	Title	Deliverable
Exposure			
3.1	ITT	Summary of Exposure	SAC
Adverse Events			
3.2	ITT	Overview of On-Treatment Adverse Events	SAC
3.3	ITT	Summary of On-Treatment Adverse Events	SAC
3.4	ITT	Summary of On-Treatment Adverse Events by Country	SAC
3.5	ITT	Summary of Post -Treatment Adverse Events	SAC
3.6	ITT	Summary of On-treatment Drug-Related Adverse Events	SAC
3.7	ITT	Summary of Serious Adverse Events (Serious, Drug-Related Serious, Fatal and Drug-Related Serious) by System Organ Class and Preferred Term (Number of Subjects and Occurrences)	SAC
3.8	ITT	Summary of On-treatment Serious Adverse Events	SAC
3.9	ITT	Summary of On-treatment Fatal Serious Adverse Events	SAC
3.10	ASE	Summary of Pre-treatment Serious Adverse Events	SAC
3.11	ITT	Summary of Pre-treatment Serious Adverse Events	SAC
3.12	ASE	Summary of Pre-treatment Serious Adverse Events Leading to Withdrawal from Study	SAC
3.13	ITT	Summary of On-treatment Drug-Related Serious Adverse Events	SAC
3.14	ITT	Summary of On-treatment Drug-Related Fatal Serious Adverse Events	SAC
3.15	ITT	Summary of On-treatment Adverse Events Leading to Permanent Discontinuation of Study Drug or Withdrawal from Study	SAC
3.16	ITT	Summary of On-treatment Adverse Events of Special Interest	SAC
3.17	ITT	Summary of On-treatment Serious Adverse Events of Special Interest	SAC
3.18	ASE	Relationship of Adverse Event System Organ Class, Preferred Term and Verbatim Text	SAC
3.19	ITT	Summary of On-Treatment Common ($\geq 3\%$ in Either Treatment Group) Non-serious Adverse Events by System Organ Class and Preferred Term (Number of Subjects and Occurrences)	SAC
3.20	ITT	Summary of the 10 Most Frequent On-treatment Adverse events in each Treatment Group	SAC

Safety Tables			
No.	Population	Title	Deliverable
3.21	ITT	Summary of On-Treatment Adverse Events by System Organ Class and Maximum Intensity	SAC
Pneumonia			
3.22	ITT	Summary of On-treatment Pneumonias Incidence	SAC
3.23	ITT	Summary of On-treatment Details of Pneumonia	SAC
3.24	ITT	Summary of Post-treatment Pneumonias	SAC
3.25	ITT	Summary of Post-treatment Details of Pneumonia	SAC
Bone Fractures			
3.26	ITT	Summary of On-treatment Bone Fractures	SAC
3.27	ITT	Summary of Post-treatment Bone Fractures	SAC
Radiography (Chest Imaging : X-Rays or CT Scan)			
3.28	ITT	Summary of On-treatment Chest Imaging (X-Ray or CT Scan	SAC
3.29	ITT	Summary of Post-treatment Chest Imaging (X-Ray or CT Scan)	SAC
Laboratory Parameters			

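### SAP 10.4.2 labels every event outside ITT as pre-treatment, so a post-dose event in a dosed subject randomised in error would carry the wrong phase

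*SAP*

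**What the plan says.** - **Phase rule.** SAP 10.4.2 sets one phase for everyone outside ITT: "Any events/assessments for subjects not in the ITT population will be assigned a Pre-treatment phase".
- **Governing principle.** SAP 10.4 introduces the phases differently: "Assessments and events will be classified according to time of occurrence relative to the start and/or stop date of the study treatment". The table in 10.4.2 follows that principle and defines pre-treatment as "Event onset date/time or assessment date/time < treatment start date/time".
- **Who is outside ITT.** SAP section 4 defines ITT as "All randomized subjects, excluding those who were randomized in error", and explains the exclusion: "A subject who is recorded as a screen or run-in failure and also randomized will be considered to be randomized in error". Dosing plays no part in the definition. Every other subject with a randomisation number stays in.
- **When dosing starts.** Protocol 6.1: "Subjects will self-administer their first dose of blinded study treatment in the clinic during Randomisation (V2". The Time and Events Table (Protocol 7.1) puts the check of the randomisation criteria at the same visit.
- **Safety population.** SAP 8.2.1 bases safety generally on ITT, as does Protocol 9.3.1. Neither document defines an all-treated set. Both give the use of the all-subjects-enrolled (ASE) population for SAEs as covering subjects who were not randomised.
- **Concomitant medication.** SAP 10.4.1 uses a different test. Its run-in-only row begins "Subject did not take study treatment (e.g. run-in failures", and the remaining rows go by dates.

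**The concern.** The sentence in 10.4.2 uses ITT membership as a stand-in for not having been treated. The two are not the same. The SAP's own definition provides for subjects who are both recorded as failures and randomised, and the first dose follows at the visit where randomisation takes place. A run-in exacerbation, an antibiotic course or a change in maintenance medication (Protocol 5.3) that comes to light after V2 could lead to a failure record for someone already dosed.

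Comparing the safety profile of the two arms is a stated objective. For such a subject the report would describe an event on study drug as having arisen before treatment. It would also leave both the event and the exposure out of the comparison between arms. A single death or drug-related SAE placed this way would be a factual error in the report.

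**Working it through.** No power, margin or variance figure bears on this point, so the check traces one subject through the rules.

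**Step 1: the subject.** Assume a subject is recorded as a run-in failure, is randomised, is dosed at V2, and has an event on Day 10 while still taking study treatment.

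- Under SAP section 4 the subject is randomised in error and so is not in ITT.
- By the dates in 10.4.2, onset falls after treatment start and no later than treatment stop + 1 day, so the phase is on-treatment.
- By the ITT sentence in 10.4.2, the phase is pre-treatment.
- Had treatment stopped earlier, the date rule could give post-treatment instead. It could not give pre-treatment.

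**Step 2: where the event lands (SAP 10.13.7, 10.13.9).**

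| Item | Appears in | Absent from |
|---|---|---|
| SAE | Table 3.10, "Summary of Pre-treatment Serious Adverse Events" (ASE); Table 3.12 (ASE) if it led to withdrawal; ASE Listings 11 and 12, plus 13 or 14; narrative (Protocol 9.4.4) | Table 3.8 and every other on-treatment table, all ITT |
| Non-serious AE | ASE Listings 11 and 12; term-mapping Table 3.18 (ASE) | Every incidence summary |
| Exposure and treatment received | Neither planned display of exposure | Table 3.1 and Listing 10 (exposure), Listing 1 (randomised and actual treatment), all ITT |

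Protocol 7.4.2.1 collects AEs only from the start of study treatment. A non-serious AE in this subject is therefore post-dose by design, yet it is labelled pre-treatment, and no pre-treatment table for non-serious AEs exists. SAP 10.13.2 adds a phase flag to listings where applicable; in this subject the flag would follow the wrong phase.

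**Step 3: which rule causes what.** Two rules act independently.

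- Correct the phase sentence only: the SAE leaves Table 3.10 but still enters no on-treatment table, because those are ITT. It would then be in no incidence table at all.
- Widen the safety population only: the event still carries the pre-treatment label, so it is still not counted as on-treatment.
- Correct both: the event is phased by date and counted.

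**Step 4: comparison with 10.4.1.** Under 10.4.1 the same dosed subject's medications would be phased by dates and could be on-treatment, while the events are pre-treatment. The mismatch would not show in the medication summaries, because Tables 1.33 to 1.40 are ITT.

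**Step 5: size.** The number of dosed subjects randomised in error is not given. For scale only, the regional counts in SAP 10.8.1 sum to 398 + 252 + 215 + 194 = 1,059, which I take as approximately the number randomised. One subject is 1/1,059 = 0.09%. Under an assumed range of 0 to 10 subjects, the share is 0% to 10/1,059 = 0.9%. Within any affected subject, all post-dose events carry the wrong phase.

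**The case against.** The strongest reply is that the case is not expected to arise. Protocol 5.4 defines screen failures as subjects who were never randomised. SAP 10.4.1 gives run-in failures as its example of people who took no study treatment, and the stated ASE use for SAEs concerns non-randomised subjects. On that view the sentence simply supplies a phase for people with no treatment start date, and 10.4.1 and 10.4.2 share one assumption. This stands as an account of the purpose, and it is why the two sections conflict only for a failure who was dosed. It does not remove the gap: SAP section 4 provides for a failure who was randomised, and nothing ties that status to not having been dosed.

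A reader might also infer three stronger things, none of which the documents support.

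- **That any ineligible subject is affected.** Ineligibility alone does not take anyone out of ITT. Table 1.10 counts eligibility deviations within ITT, and SAP 10.1.2 handles unmet eligibility or randomisation criteria as exclusions from mPP. Those subjects' events are phased by date and appear in the on-treatment tables.
- **That the phase sentence by itself keeps the event out of the on-treatment tables.** The ITT restriction, which Protocol 9.3.1 prespecified, already does so.
- **That the event disappears from the report.** ASE Listings 11 to 14 and the narratives still show it. The fault is a wrong label and omission from the summaries.

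**Conclusion.** The rule is wrong as written, within a narrow scope. It gives a factually incorrect phase to post-dose events in subjects who were recorded as a screen or run-in failure, randomised, and actually dosed. For them, an SAE is tabulated as pre-treatment and missing from every on-treatment table, and a non-serious AE reaches no incidence summary.

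The group may be empty; the documents support no figure above zero. The conclusion rests on two assumptions: that the SAP's definition of randomised in error is applied literally, and that a failure can be recorded after the V2 dose. No efficacy analysis is touched. The point is worth correcting because the error would be complete for any subject it reaches and the remedy is small.

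**What to change.** 1. **Phase rule.** In SAP 10.4.2, replace the ITT sentence with one that assigns the pre-treatment phase only to subjects who took no study treatment. Phase every subject who took at least one dose by treatment start and stop dates, in ITT or not.
2. **Safety displays.** Base the exposure and on-treatment safety displays (AEs, laboratory, vital signs, ECG) on all subjects who took at least one dose. If ITT is kept for these displays, add an ASE-based table of on-treatment AEs and SAEs, with an exposure listing, for dosed subjects outside ITT.
3. **Efficacy.** Leave ITT and mPP unchanged.
4. **Record.** An all-treated safety set departs from Protocol 9.3.1, so list it in SAP 2.1 among the changes to the planned analysis, before unblinding.

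The cost is one sentence of SAP wording and a treated-subject flag in the safety programs, with no new data. The drawback is that the safety denominator may differ from ITT by a few subjects, so the tables need a footnote. If no subject meets the description, the on-treatment counts stay as they are.
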